6.13.3.4 Dose Response Relationship with 3 Dose Levels of Mesdopetam

The dose response relationship will be explored by first considering the significance of the treatment effect in the primary model and then by visually assessing the relationship using line plots of LS mean ($\pm 95\%$ CI) over time. If a significant effect is observed, a Jonckheere-Terpstra (JT) trend test may be performed using the contrast statement in PROC GLM to construct a T trend statistic to test a one-side hypothesis for increasing trend. If a normal distribution of values is not observed, a non-parametric approach may be pursued. However, if a significant treatment effect is not observed, or there is a significant departure from a linear trend between doses, a test for trend will not be performed.

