6.2. Rationale for study design and dose selection

The pharmacological effects of mesdopetam have been evaluated in a range of preclinical animal models. Integrating the preclinical *in vivo* data and *in vitro* assessments for the main molecular target, the dopamine D3 receptor, indicates that efficacy in patients with PD could be expected at doses producing 100-200 nM in plasma concentration.

Individualized dosing has been explored in two previous clinical studies (phase 1b and phase 2a). In this phase 2b study a dose-response analysis will be performed to evaluate three dose levels of mesdopetam (i.e. 2.5 mg, 5 mg and 7.5 mg b.i.d.). The dose-response analysis will give knowledge of the relationship among dose, drug-concentration in blood and clinical response (effectiveness & safety). The dose levels to be used in this study have been selected based on previous clinical studies (see Section 4.6) where data indicates that clinically relevant efficacy may be achieved at the dose levels selected. The most commonly reported AE in patients randomized to mesdopetam in the phase 2a study was increased parkinsonism (during titration phase), and the finding of a possible dose dependent increase in OFF time strongly suggest that lower doses than 10 mg b.i.d. should be explored in this forthcoming study. The finding of a strong trend towards improved general motor function in patients allocated to 7.5 mg b.i.d. or lower indicate that the efficacy of mesdopetam may extend beyond that of reducing ON-phase dyskinesia.

6.3.Discussion of study design, including the choice of control groups

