The study has a parallel group design, which is deemed more appropriate than a cross-over considering the aetiology of the illness. The study will be double blind and placebo controlled. Patients will be randomized, in equal proportions, to placebo or to one of the three doses (2.5 mg, 5 mg or 7.5 mg b.i.d.) of the active dose regimen (mesdopetam), to permit analyses of the dose response relationship. For patients to adjust to the new medication, IMP treatment will start with a run-in period of one week. During this initial week, patients randomized to mesdopetam will receive 5 mg b.i.d. and patients randomized to placebo will receive placebo b.i.d. Results from previous clinical studies show that 5 mg b.i.d. is well tolerated by a vast majority of patients. Following the initial one-week run-in, patients randomized to mesdopetam will continue with their assigned dose (2.5 mg, 5 mg, or 7.5 mg b.i.d.) and patients randomized to placebo will continue with placebo.

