14.1. General considerations

A single analysis at the conclusion of the investigation is planned and there will be no interim analyses.

All data will be described and analyzed according to allocated treatment group (mesdopetam 2.5 mg, 5 mg, 7.5 mg and placebo b.i.d.), and visit. In addition, PK data will also be described and analyzed according to time-point, as appropriate (pre and post dose). Each data summary will be supported by individual patient listings.

All quantitative, continuous data will be summarized by the number of non-missing observations, mean, median, standard deviation, and minimum and maximum for both actual values and, for all data except PK assessments, change from baseline data. All categorical (qualitative binary, ordinal) data will be summarized by presenting the frequency and percent. Percentages will be based on the number of non-missing observations or the patient population unless otherwise specified. For each variable, all categories will be shown. Zero frequencies (but not the percent) within a category will be presented.

Statistical methods applied will be appropriate to the nature and distribution of the data. A (two-sided) significance level of 5% (<0.05) will be implemented throughout and in view to the stage of development of the drug no statistical adjustment for multiplicity of analysis testing performed is planned. Graphical displays will be used to support the findings wherever possible. All will use two-sided 95% confidence intervals to allow estimation of the minimum likely effect size, which will be useful when moving the development programme forward to Phase III.

The null hypothesis assumed throughout is that there is no difference between the active treatment and the control for any comparison performed (mesdopetam vs placebo). The alternative hypothesis is that there is in fact a difference and this may be in either direction in favour of active or the control.

Baseline will be defined as the last non-missing assessment (either scheduled, unscheduled or repeat) that is completed prior to dosing. Baseline average daily time spent for each patient will be calculated by taking the arithmetic mean of daily time spent in each state from the three 24-hour patient home diaries completed before the baseline visit.

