2.2 Secondary Objectives

- To establish the dose response relationship with 3 dose levels of mesdopetam.
- To evaluate the effects of mesdopetam on severity of ON-phase dyskinesia and motor symptoms of PD.
- To evaluate the effects of mesdopetam on the daily hours spent in different motor states.
- To evaluate the safety and tolerability of mesdopetam given twice daily during 84 consecutive days.
- To evaluate trough and 2-hour post dose plasma concentrations of mesdopetam and its two main metabolites (IRL902 (N-dealkylated) and IRL872 (acetylated)).

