6.12 Primary Efficacy Analyses

All applicable statistical tests will be performed at a local significance level consistent with an overall FWER of 5% and the multiple testing strategy described in Section 0. All comparisons between treatments will be reported with 95% confidence intervals (CI) for the difference. All efficacy analyses will be performed by randomized treatment group and adjusted dose group for patients in the FAS, as well as all active doses grouped compared to placebo.

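### The only efficacy trend test for the first secondary objective is optional, conditional on undefined criteria, one-sided without a stated alpha, and misnamed

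*SAP*

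**What the plan says.** The first secondary objective, in Protocol 5.2 and SAP 2.2, is "To establish the dose response relationship with 3 dose levels of mesdopetam". Protocol 6.3 explains that equal allocation to placebo and three doses was chosen "to permit analyses of the dose response relationship". Protocol 6.2 makes a commitment: "In this phase 2b study a dose-response analysis will be performed to evaluate three dose levels of mesdopetam".

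SAP 6.13.3.4 carries this out in three steps: consider the significance of the treatment effect in the primary model, look at LS-mean plots, and then possibly test for trend. On the test it says "If a significant effect is observed, a Jonckheere-Terpstra (JT) trend test may be performed using the contrast statement in PROC GLM", and that this is done "to construct a T trend statistic to test a one-side hypothesis for increasing trend". An unnamed non-parametric approach may be used if the data are not normal. No trend test is done "if a significant treatment effect is not observed, or there is a significant departure from a linear trend between doses".

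On error rates, Protocol 14.1 says "A (two-sided) significance level of 5% (<0.05) will be implemented throughout", with an alternative in either direction. SAP 6.12 ties tests to local levels derived from the multiplicity strategy. SAP 6.15 sets out that strategy for the primary and two key secondary endpoints and gives the trend test no place. SAP 9, the list of changes from the protocol, has no entry for a one-sided trend test.

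**The concern.** Four things are left open or are inconsistent.

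1. **Whether the test is run.** The wording is permissive even when both conditions are met.
2. **The conditions.** A significant effect in the primary model could mean 7.5 mg against placebo, any dose, the pooled contrast or an overall treatment test. Departure from linearity could be judged over all four arms or over the three active doses. No test or level is named for it.
3. **The level.** A one-sided test with no alpha could be run at 5% or 2.5%. Protocol 14.1 points to two-sided 5%; the SAP's local-level rule supplies no figure.
4. **The method.** Jonckheere-Terpstra is a rank test against ordered alternatives and needs only monotone order, so a linearity condition does not suit it. A PROC GLM contrast is a parametric comparison of means. It is also not the primary MMRM, and the section does not say which visit it uses or how it treats missing data.

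These choices could be made after unblinding. They decide whether a trend p-value exists and what it means. A p-value reported only after a favourable dose comparison cannot be read at face value.

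**Working it through.** **Inputs.** 31 evaluable per arm, SD 3.5 h and a 3 h difference (SAP 4; Protocol 14.2). Assumed: normal data, no covariate gain, pooled variance on 4 × (31 − 1) = 120 df. Effect patterns are hours over placebo at 2.5/5/7.5 mg and are also assumptions.

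**The plan's own figure.** SE = 3.5 × √(2/31) = 0.889 h; 3/0.889 = 3.375; power = Φ(3.375 − 1.960) = 92.1%, matching the stated 92%. No figure is given for the trend test.

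**Trend statistic.** With coefficients (−3, −1, 1, 3) for placebo, 2.5, 5 and 7.5 mg: L = Σcᵢȳᵢ / (s√(20/n)).

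**Linearity condition, two readings at 5%.**
- Four arms: lack-of-fit F on 2 and 120 df. For 3/3/3 h the fitted line gives residuals −0.9, 1.2, 0.3, −0.6, sum of squares 2.70, so the noncentrality is 31 × 2.70/12.25 = 6.8.
- Three active doses: contrast (1, −2, 1). For 3/3/3 h this is 3 − 6 + 3 = 0, so there is no departure to detect.

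Share of trials in which the trend test is withheld, among those with 7.5 mg significant (simulation):

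| Pattern (h) | Four arms | Three active doses |
|---|---|---|
| 3/3/3 | 64% | 5% |
| 0/0/3 | 64% | 51% |
| 2/2/2 | 35% | 5% |
| 0.67/1.33/2 | 5% | 5% |

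At 35 per arm (154 × 0.9/4 ≈ 35) the four-arm column becomes 70%, 70%, 38% and 5%.

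**Effect condition.** Chance that the one-sided trend test rejects, given that the effect condition is met. It is read three ways: 7.5 mg significant in favour of drug / any dose so / overall 3-df F, each at 5%.

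| Pattern (h) | One-sided 5% | One-sided 2.5% |
|---|---|---|
| Null | 92/46/24% | 71/32/19% |
| 2/2/2 | 97/79/86% | 88/67/77% |
| 0.67/1.33/2 | 99/96/98% | 95/91/96% |

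If the 7.5 mg condition is two-sided, the null figure at one-sided 5% is 46% instead of 92%. The unconditional null rate (condition met and trend significant) is at most 2.9%.

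**Trends that would go unreported.** Share of trials with a favourable two-sided 5% trend but the effect condition not met, same three readings: 7/5/20% for linear 2 h, 10/3/16% for 1/2/2 h, 3/<1/9% for 2/2/2 h.

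**The case against.** The strongest reply is that little depends on this test. SAP 6.13.3.4 says the relationship is explored, and the test sits among the other secondary analyses, outside the hierarchy. The protocol promises a dose-response analysis, not a trend test. Per-dose estimates against placebo and LS-mean plots are produced regardless (SAP 6.12.3), and SAP 6.12.5.3 adds a mandatory MMRM by adjusted dose group. This stands, and it limits the weight of the point. It does not define the trend test, and the objective is worded as establishing the relationship.

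Further points stand in part:
- The effect condition is anchored to the primary model, where Week 12 is the timepoint of interest and 7.5 mg is tested first. That suggests a default reading, but the section does not state one.
- The 92% null figure needs a favourable 7.5 mg result; the two-sided reading gives 46%. Either is far from a nominal 5%.
- A 3 h plateau is not the shape the sponsor expects, since 7.5 mg is hypothesised to be most efficacious. If the truth is linear, both linearity readings withhold only about 5%. But dose shape is what the objective sets out to learn.
- The 35-per-arm figures assume 10% dropout, and SAP 4 says dropout exceeded expectation. They are an optimistic bound.
- The missing entry in SAP 9 is a weak point, because the protocol specified no trend test to change. The conflict with two-sided testing throughout remains.

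**Conclusion.** The concern holds. The test is optional, its two conditions are not operational, its sidedness conflicts with Protocol 14.1, its alpha is unstated, and its name does not match its method. The consequence is minor to moderate: no primary or key secondary conclusion can change, and unconditional type I error is not inflated. What suffers is the answer to the first secondary objective. Under a 3 h plateau, one unstated choice moves the share of withheld trend tests from 5% to 64%. Under a linear 2 h effect, 5% to 20% of trials would leave a favourable trend unreported, depending on how the effect condition is read. These figures rest on 31 per arm, SD 3.5, normal data without covariate adjustment, and the readings and effect patterns stated above.

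**What to change.** In SAP 6.13.3.4 keep the first sentence and replace the rest, including the non-parametric fallback, with:

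> A two-sided linear dose contrast at Week 12 from the primary MMRM (randomized dose) will always be computed and reported with estimate, 95% CI and nominal p-value, outside the hierarchy of Section 6.15. Departure from linearity will be described and will not decide whether the contrast is reported.

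In the arm order of the SAP 6.12.3 code:

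`LSMESTIMATE TRT01PN*AVISITN 'Linear trend at Week 12' 0 0 -1 0 0 1 0 0 3 0 0 -3 divisor=10 / CL e OM;`

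The divisor is Σcx for c = (−3, −1, 1, 3) and x = (0, 1, 2, 3), that is 0 − 1 + 2 + 9 = 10, so the estimate is in hours per 2.5 mg b.i.d. step. Confirm in programming that the active arms are coded in ascending order. Keep the per-dose estimates and plots, because the contrast shows trend and not shape. The general provision in Protocol 14.9 for failed model assumptions still applies.

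If a rank check is wanted, run Jonckheere-Terpstra in PROC FREQ as a sensitivity analysis on numeric dose (0, 2.5, 5, 7.5). Do not use TRT01PN: the sample code makes placebo the fourth level, so the test would rank it above 7.5 mg.

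**Cost.** One line of SAS, two sentences and no new data. It adds one nominal p-value, reported even when unfavourable. Two-sided power is 65% for linear 2 h. For 2/2/2 h it is 56%, below the 61% for 7.5 mg alone. For an inverted U (1/2/1 h) it is only 29%, where at least one dose is significant in 66% of trials. Precision: SE = 3.5 × √(20/31)/10 = 0.281 h, so the 95% CI half-width is 1.98 × 0.281 = 0.56 h per step (0.52 h at 35 per arm).

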6.13.3.5 Average Daily Hours Spent in Different Motor States

Descriptive statistics for the average daily hours and change from baseline by visit will be provided for each motor state (ON-time without troublesome dyskinesia, ON-time with troublesome dyskinesia, OFF-time, and asleep). Additionally, average daily total ON-time (defined as the sum of ON-time with and without troublesome dyskinesia) will be summarized. Change from baseline in average daily hours for each motor state will be analysed and reported in the same manner as for the primary analysis, as described in Section 6.12.3.

Boxplots showing the distribution of values (minimum value, first quartile, median, third quartile and maximum value) for each motor state will be presented by treatment group and visit. If the presence of outliers affects the interpretation of the distribution, boxplots showing 1.5* interquartile range (IQR) may be shown.

A line chart showing the change from baseline in mean (\pm SD) hours spent in each motor state (ON-time without troublesome dyskinesia, ON-time with troublesome dyskinesia, OFF-time) will be presented by treatment group and visit (one panel per visit). A separate line chart will also be presented as above, showing the change in daily total ON-time (defined as the sum of ON-time with and without troublesome dyskinesia) versus the change in daily OFF-time.

A stacked bar chart will be produced showing the mean percentage of time spent in each motor state during the day (ON-time without troublesome dyskinesia, ON-time with troublesome dyskinesia, OFF-time, or asleep) by treatment group and visit (one panel per visit).

QMD Ref: Worldwide-TMP-ST-005-7.0 Effective: 12Aug2019	Governing QMD: Worldwide-SOP-ST-001	
Confidentiality Statement		
This document is the property of Worldwide Clinical Trials Inc. and may not be duplicated, copied, altered or removed from company without prior approval from Worldwide Quality Assurance or in compliance with Worldwide Standard Operating Procedures.		
REF: Worldwide-TMP-QA-001f-1.3	Page 37 of 49	

Worldwide Clinical Trials Controlled Quality Management Document		
WORLDWIDE CLINICAL TRIALS	Sponsor:	Integrative Research Laboratories Sweden AB
CLINICAL TRIALS	Protocol Number:	IRL790C005
STATISTICAL ANALYSIS PLAN. PHASE 2-3-4		

6.13.3.6 ON-Phase Dyskinesia, Clinician's Global Impression of Severity

Severity of the patient's ON-phase dyskinesia will be rated by the investigator, considering his or her total clinical experience with the PD population, using the CGI-S scale. Severity will be rated based on a 1–7-point weighted scale ranging from "normal", not at all ill" (1) to "among the most extremely ill patients" (7).

CGI-S of ON-phase dyskinesia will be completed at all in-person visits up to end of treatment, including baseline. A shift table for the change from baseline in number and percent of patients rated in each score category (1 to 7) will be presented by treatment group and visit. Percentages will be based on the number of patients with non-missing score at baseline and post-baseline for the relevant visit. Descriptive statistics for the score as a continuous measure for observed values and change from baseline to each post-baseline visit will also be provided.

Change from baseline with mesdopetam compared to placebo in CGI-S of ON-phase dyskinesia will be analysed as a continuous variable using a MMRM, conducted in the same manner as for the primary analysis, and reported (including model estimates and line plot) as described in Section 6.12.3.

6.13.4 Motor Examination, MDS-UPDRS - Part 3 Total Score

MDS-UPDRS Part 3 total score, will be summarized by treatment group and visit. Change from baseline will be summarised, analysed, and reported (including model estimates and line plot) in the same manner as for the primary analysis, as described in Section 6.12.3.

6.14 Exploratory Efficacy Analyses

All exploratory efficacy analyses will be performed on the FAS for all dose levels of mesdopetam (2.5 mg b.i.d., 5.0 mg b.i.d., 7.5 mg b.i.d., and pooled) and placebo.

6.14.1 Overall PD Symptoms, Clinician's Global Impression of Severity

Severity of the patient's PD will be rated by the investigator, considering his or her total clinical experience with the PD population, using the CGI-S scale. CGI-S of the patient's overall PD symptoms will be completed at all in-person visits up to end of treatment, including baseline. Actual scores and changes in scores will be summarized, analysed, and reported by visit and treatment group as described in Section 6.13.3.6.

QMD Ref: Worldwide-TMP-ST-005-7.0 Effective: 12Aug2019	Governing QMD: Worldwide-SOP-ST-001	
Confidentiality Statement		
This document is the property of Worldwide Clinical Trials Inc. and may not be duplicated, copied, altered or removed from company without		
prior approval from Worldwide Quality Assurance or in compliance with Worldwide Standard Operating Procedures.		
REF: Worldwide-TMP-QA-001f-1.3	Page 38 of 49	

Worldwide Clinical Trials Controlled Quality Management Document		
	Sponsor:	Integrative Research Laboratories Sweden AB
CLINICAL TRIALS	Protocol Number:	IRL790C005
STATISTICAL ANALYSIS PLAN. PHASE 2-3-4		

6.14.2 Cognitive Function, Mini-Mental State Examination

Descriptive statistics for the MMSE total score at each visit (Baseline, Visit 5 (Week 12)) and the change from baseline will be provided per treatment group.

Change from baseline to Week 12 with mesdopetam compared to placebo in the MMSE total score will be analysed using an ANCOVA. The model will include randomized treatment as a factor, and the baseline value for average daily ON time without troublesome dyskinesia (hours) as a continuous covariate. The LS mean estimate, SE, and 95% CI, for each treatment group as well as the estimated treatment difference for each dose level compared to placebo, corresponding SE and p-value will be obtained from the model.

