11.2.4.4. Mini-Mental State Examination (MMSE)

The MMSE will be administered at screening and at Visit 5 (EOT).

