14.9.1. Primary analyses

Per protocol, patients will be required to complete three 24-hour patient home diaries prior to Baseline (Visit 1), and Visits 3, 4 and 5 (EOT). Average daily ON-time without troublesome dyskinesia will be calculated by taking the arithmetic mean of daily ON-time without troublesome dyskinesia reported in each individual diary at each visit. Change from Baseline will be calculated by subtracting the mean values at each visit (Visits 3, 4 and 5 (EOT)) from the Baseline mean value for each individual patient.

The primary endpoint will be analyzed using a mixed model repeated measures (MMRM) analysis that includes all average daily ON-time without troublesome dyskinesia changes from baseline to Week 4 (Visit 3) through to Week 12 (Visit 5/EOT) for all patients in the FAS. The model will include randomized treatment, visit (Visits 3, 4 and 5/EOT), and treatment by visit interaction as explanatory, fixed effect variables. Baseline value for average daily hours of ON-time without troublesome dyskinesia will be included as a continuous covariate along with the baseline stratification factor of daily hours spent in ON-time with troublesome dyskinesia (<6 hours and \geq 6 hours).

The treatment by visit interaction will remain in the model regardless of significance. The patient effect will be assumed to be random and an unstructured covariance structure will be assumed for within patient variation.

The main comparison will be a contrast between treatment groups at EOT (Visit 5, Week 12). Estimates for each individual dose level, as well as all active doses grouped vs. placebo will be obtained from the model. Least squares means, 95% confidence intervals, and p-values of the treatment comparisons along with basic arithmetic summary statistics (mean, median, standard deviation, min and max) will be provided.

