14.9.1. Secondary analyses

All secondary and exploratory efficacy endpoints (including CGI-S data) will be analyzed per the Primary efficacy endpoint for all patients in the FAS. Summary statistics (mean, median, standard deviation, min and max), least squares means, 95% confidence intervals, and p-values of the treatment comparisons will be provided for descriptive purposes.

Where appropriate, alternative methods suited to the distribution of data may be applied. Full details will be provided in the SAP.

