6.2.2 Baseline

Baseline is defined as the last non-missing value (either scheduled, unscheduled or repeat) before the patient receives the first dose of study drug.

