Demographic and baseline characteristic summaries will be presented by treatment group and overall, based on the randomized treatment group for the FAS and the SAS. If these sets are equal, only the FAS will be presented. All collected data will be listed. Summaries will be presented for the following variables:

Demographic Data

- Age at Screening (years)
- Age by category (< 65 years and \geq 65 years)
- Gender
- Fertility status (female only)
- Ethnicity
- Race (where more than one race is selected the patient will be presented under the 'Multiple races' category in the summary but each selected race will be identified in the listing).

Baseline Characteristics

- Weight at Screening (kg)
- Height at Screening (cm)
- BMI at Screening (kg/m²)

Clinical Characteristics

- Hoehn and Yahr Scale
- Years from PD diagnosis at baseline and will be calculated as follows: Years from PD Diagnosis at Baseline = (Day 1 - Start Date of PD from the medical history) / 365.25. If the start date of PD is partial, then only year portion will be used for calculation and will follow Section 6.3.5 for rounding of decimals
- Average levodopa dose based on evaluable reported usage (in mg) taken on or after first dose of study drug

QMD Ref: Worldwide-TMP-ST-005-7.0 Effective: 12Aug2019	Governing QMD: Worldwide-SOP-ST-001
Confidentiality	y Statement
This document is the property of Worldwide Clinical Trials Inc. and may not be duplicated, copied, altered or removed from company without	
prior approval from Worldwide Quality Assurance or in compliance with Worldwide Standard Operating Procedures.	
REF: Worldwide-TMP-OA-001f-1 3	Page $24 \text{ of } 49$

- ON-time (hours) with troublesome dyskinesia
- Randomisation strata (<6 hours or \geq 6 hours of ON-time with troublesome dyskinesia)
- MDS-UPDRS question 4.2 score (functional impact of dyskinesias)
- MMSE at Baseline
- Physical examination by body system at baseline

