6.12.5.2 ANCOVA Analysis

An analysis of covariance (ANCOVA) will also be performed using the FAS. The ANCOVA model will be adjusted for the following covariates: randomized treatment, baseline value for average daily hours of ON time without troublesome dyskinesia (continuous covariate), as well as randomisation stratification factor for daily hours spent in ON-time with troublesome dyskinesia (<6 hours, \geq 6 hours). The dependent variable is the change from baseline in average daily ON-time (hours) at Week 12. Missing observations will not be imputed.

The LS means, SEs, and 95% CIs will be provided for each treatment group, as well as treatment difference estimates, SEs, and p-values for each dose level and combined dose groups compared to placebo.

The following is the sample SAS code that will be used to implement this analysis:

```
PROC MIXED DATA= DATAIN;
CLASS TRT01PN STRATF;
MODEL CHG_WEEK12 = TRT01PN BASE STRATF / SOLUTION;
LSMEANS TRT01PN / CL DIFF OM;
LSESTIMATE TRT01PN "Difference at Week 12" 1 1 1 -3 / CL e OM;
LSESTIMATE TRT01PN "Combined at Week 12" 1 1 1 0 / CL e OM;
RUN;
```

Where TRT01PN = Planned Treatment Group Number; BASE = Baseline Value; CHG_WEEK12 = Change from Baseline at Week 12; STRATF = Stratification Factor.

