9 CHANGES TO PLANNED PROTOCOL ANALYSIS

- 1. The primary efficacy analysis will be adjusted for country and weighted by the number of subjects participating from each country to account for any observed imbalances in recruitment across countries.
- 2. Analyses will be conducted for individual active dose and pooled doses.
- 3. Secondary and exploratory endpoints have been itemized separately compared to the protocol for clarity.
- 4. Key Secondary Efficacy Endpoints were defined:
 - Change from baseline with mesdopetam compared to placebo in ON-phase dyskinesia assessed by MDS-UPDRS part 4 question 4.2 (Functional impact of dyskinesias).
 - Change from baseline with mesdopetam compared to placebo in disability associated with ON-phase dyskinesia assessed with the sum score of parts 1b and 4 of the UDysRS.
- 5. Other Key Secondary Efficacy Endpoints were defined:
 - Change from baseline with mesdopetam compared to placebo in motor symptoms of PD assessed with MDS-UPDRS total score of part 2 (M-EDL).
 - Change from baseline with mesdopetam compared to placebo in average daily OFF-time.
- 6. Exploratory endpoint added to reflect protocol section 14.7. Efficacy endpoints, Table 6 Other endpoints:
 - Change from baseline with mesdopetam compared to placebo in the total scores for each component part of the MDS-UPDRS (Part 1, Part 3, and Part 4).
 - Change from baseline with mesdopetam compared to placebo in freezing and freezing of gait, assessed by MDS-UPDRS: Question 2.13 + Question 3.11.
- 7. Safety endpoint added to reflect protocol section 14.7. Efficacy endpoints, Table 6 Other endpoints:
 - Change from baseline with mesdopetam compared to placebo in features of dopamine dysregulation syndrome assessed by MDS-UPDRS Question 1.6.
- 8. Improvement in Daily ON-time, Responder Analysis
- 9. PK Analysis Set was defined.
- 10. CYP Genotype Subset was defined.
- 11. Multiplicity strategy was refined to address Key Secondary Endpoints.

QMD Ref: Worldwide-TMP-ST-005-7.0 Effective: 12Aug2019	Governing QMD: Worldwide-SOP-ST-001	
Confidentiality Statement		
This document is the property of Worldwide Clinical Trials Inc. and may not be duplicated, copied, altered or removed from company without		
prior approval from Worldwide Quality Assurance or in compliance with Worldwide Standard Operating Procedures.		

Worldwide Clinical Trials Controlled Quality Management Document		
WORLDWIDE CLINICAL TRIALS	Sponsor:	Integrative Research Laboratories Sweden AB

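### The MMSE change model adjusts for baseline diary ON-time instead of baseline MMSE, and leaves out the randomisation stratum

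*SAP*

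**What the plan says.** SAP 6.14.2 fits an ANCOVA to the change in MMSE total score from baseline to Week 12. The model contains randomised treatment and the "baseline value for average daily ON time without troublesome dyskinesia (hours) as a continuous covariate", and nothing else.

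Other parts of the plan bear on this:

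- **SAP 6.12.5.2**, the SAP's other Week 12 ANCOVA (for the primary endpoint), is coded as "MODEL CHG_WEEK12 = TRT01PN BASE STRATF / SOLUTION". BASE is the baseline of the variable being analysed and STRATF is the randomisation stratum.
- **Protocol 14.9.1, Secondary analyses**, sets this rule: "All secondary and exploratory efficacy endpoints (including CGI-S data) will be analyzed per the Primary efficacy endpoint for all patients in the FAS".
- **Protocol 14.9.1, Primary analyses:** the baseline of the analysed diary variable "will be included as a continuous covariate along with the baseline stratification factor".
- **Availability of baseline MMSE:** Protocol 11.2.4.4 schedules the MMSE at screening and Visit 5. SAP 6.2.2 states: "Baseline is defined as the last non-missing value (either scheduled, unscheduled or repeat) before the patient receives the first dose of study drug". The screening score meets this definition, and SAP 6.6 tabulates "MMSE at Baseline".
- **SAP section 9** ("CHANGES TO PLANNED PROTOCOL ANALYSIS") goes down to exploratory level, including the responder analysis, but has no entry for the MMSE model.

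**The concern.** A model for change in a score normally adjusts for the baseline of that score. Change is usually negatively correlated with its own baseline, through regression to the mean, and this adjustment removes that part of the variance. Diary hours of good ON-time are a different measurement, and the SAP gives no reason to expect them to predict change in MMSE. The covariate wording follows the primary model closely, so it looks carried over rather than chosen.

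The missing stratum is a separate inconsistency. Randomisation was stratified on <6 versus >=6 hours of ON-time with troublesome dyskinesia, and both the protocol's primary model and SAP 6.12.5.2 include that factor.

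MMSE is the only endpoint serving the cognitive-function objective. At stake is the precision of its treatment comparisons and their exposure to chance differences in baseline MMSE between arms of about 31 to 38 patients. Type I error is not at stake, and neither is any primary or key secondary conclusion.

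The use of ANCOVA rather than MMRM is not criticised: MMSE has one post-baseline assessment.

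**Working it through.** **1. Model terms side by side**

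| Model | Baseline covariate | Stratum |
|---|---|---|
| Protocol primary MMRM | analysed variable's own | yes |
| SAP 6.12.5.2, Week 12 ANCOVA | analysed variable's own | yes |
| SAP 6.14.2, MMSE ANCOVA | another variable's (diary hours) | no |

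Both differences are plain from the text. The plan states no power, SD or expected effect for MMSE, so it has no figure of its own to reproduce here.

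**2. Precision**

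Assumptions: equal SD s at screening and Week 12, correlation r between the two scores, and diary hours unrelated to MMSE change.

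- Variance of change without own-baseline adjustment: 2s²(1 − r)
- Variance of change given baseline MMSE: s²(1 − r²)
- Proportion of variance saved: 1 − (1 + r)/2 = (1 − r)/2
- Reduction in SE: 1 − √((1 + r)/2)

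| r | Unadjusted | Adjusted | Variance saved | SE reduction |
|---|---|---|---|---|
| 0.5 | 1.00 s² | 0.75 s² | 25% | 13% |
| 0.7 | 0.60 s² | 0.51 s² | 15% | 8% |
| 0.9 | 0.20 s² | 0.19 s² | 5% | 3% |

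A simulation of the four-arm model with 31 patients per arm gave ratios of the SD of the estimate (as written to own-baseline adjusted) of 1.15 at r = 0.5 and 1.10 at r = 0.7. The formula, √(2/(1 + r)), gives 1.15 and 1.08.

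**3. Effect of excluding MMSE below 24 at screening**

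This exclusion narrows the baseline spread. Let the baseline variance be t·s², and hold the slope of Week 12 on baseline (r) and the residual variance s²(1 − r²) fixed, which requires a linear relation. The saving is then (1 − r)²t / [(1 − r)²t + 1 − r²]. With t = 0.5 (assumed):

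- r = 0.5: 0.125/(0.125 + 0.75) = 14%
- r = 0.7: 0.045/(0.045 + 0.51) = 8%
- r = 0.9: 0.005/(0.005 + 0.19) = 3%

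**4. Chance imbalance**

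The slope of change on baseline is r − 1. Without adjustment, a share 1 − r of any between-arm difference in mean baseline MMSE passes into the treatment difference: 50%, 30% or 10%. The sign is negative, so an arm that starts higher looks worse. The share is the same in the restricted case of step 3.

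The SD of the chance difference in mean baseline between two arms, in baseline SDs, is √(2/n):

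- n = 31, the evaluable number per arm in SAP section 4: 0.254
- n = 38, from 154/4 = 38.5 with no dropout: 0.229

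A one-SD chance imbalance therefore shifts the estimate by between 0.5 × 0.254 = 0.127 and 0.1 × 0.229 = 0.023 baseline SD.

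**The case against.** **The protocol leaves room.** The same protocol subsection allows alternative methods that suit the distribution of the data and leaves the details to the SAP. Read literally, analysing MMSE as the primary endpoint is analysed could even mean keeping diary hours as the covariate. This has some weight: the protocol is clearly contradicted only on the stratum. But the leeway concerns distribution. It explains ANCOVA in place of MMRM, not an unrelated covariate or a dropped stratum, and the SAP gives no distributional reason for either.

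**The stratum half shows no consequence.** This stands. No gain is claimed for the stratum, and the SAP is not uniform: the responder test in 6.14.3 is also unstratified, and the SAP's primary MMRM includes country, which 6.12.5.2 omits. The stratum is added for consistency with the protocol's primary model and 6.12.5.2.

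**The sizes rest on assumptions.** This also stands. No MMSE SD or correlation is documented, and the 25%, 15% and 5% savings are the favourable case compared with the restricted one. The 38 per arm is a zero-dropout upper bound, and SAP section 4 reports higher dropout than expected. At 10% dropout, 38.5 × 0.9 = 34.65 per arm and √(2/34.65) = 0.24, so little changes. The 31 is planned for the primary endpoint and is not a strict lower bound for MMSE.

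**The impact is very low.** Agreed. Baseline MMSE by arm and the MMSE descriptives will be reported, so an imbalance would be visible. The planned estimate would still not be corrected for it.

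**Conclusion.** The concern holds and is minor. The MMSE model uses the wrong baseline and omits the stratum, without a stated reason or an entry in section 9. Randomisation protects validity; the cost is efficiency and exposure to chance imbalance. Across the assumed correlations of 0.5 to 0.9, the avoidable variance runs from 25% down to 5%, or from 14% down to 3% if the screening cut-off halves the baseline variance. A typical chance imbalance would move the estimate by 0.13 to 0.02 baseline SD. These sizes depend on the assumed correlation, equal SDs (in the unrestricted case), linearity and uninformative diary hours. The finding that the covariate does not match the outcome rests on the text alone. The endpoint is exploratory and outside the hierarchy in SAP 6.15, so no confirmatory conclusion is affected.

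**What to change.** Replace the model sentence in SAP 6.14.2 with:

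> Change in MMSE total score at Week 12 will be modelled with randomised treatment and the randomisation stratum (<6 hours, >=6 hours) as factors and baseline MMSE total score (Section 6.2.2) as a continuous covariate. Each dose level, and the three doses pooled, will be compared with placebo.

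The pooled comparison is already required by SAP 6.13.3.3 and 6.14; 6.14.2 does not mention it. Code it as the contrast 1 1 1 -3 on TRT01PN with divisor = 3. The 6.12.5.2 code lacks the divisor and would return three times the pooled difference. That code also writes LSESTIMATE where 6.12.3 writes LSMESTIMATE, so it should not be copied unchanged. Country can stay out, as in 6.12.5.2.

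Add one line to section 9 recording the MMSE model. If the sponsor prefers to keep diary hours, section 9 should give the reason.

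Cost: one sentence and one line. All variables are already collected. Swapping the covariate uses no extra degree of freedom; adding the stratum uses one.
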